 - 3.2.3. after 12 weeks of therapy.
- 4. Proportion of subjects with lack of anxiety (<14 points according to HAM-A scale):
 - 4.1. group 1 (Tenoten® 4 tablets a day)
 - 4.1.1. after 4 weeks of therapy
 - 4.1.2. after 8 weeks of therapy
 - 4.1.3. after 12 weeks of therapy
 - 4.2. group 3 (Tenoten® 8 tablets a day)
 - 4.2.1. after 4 weeks of therapy
 - 4.2.2. after 8 weeks of therapy
 - 4.2.3. after 12 weeks of therapy.
- 5. Change from baseline in total EQ-5D-3L score after 12 weeks of treatment.
 - 5.1. group 1 (Tenoten® 4 tablets a day)
 - 5.2. group 3 (Tenoten® 8 tablets a day).
- 6. Total CGI score:
 - 6.1. group 1 (Tenoten® 4 tablets a day)
 - 6.2. group 3 (Tenoten® 8 tablets a day).

Safety assessment

- Occurrence and nature of adverse events, their intensity (severity), causal relationship to the study drug, and outcome.
- Changes in vital signs during the treatment.

Study design

Design – an international multicenter, randomized, double-blind, placebo-controlled parallelgroup clinical trial to evaluate efficacy and safety of various schemes of Tenoten \mathbb{R} in the treatment of anxiety.

The study will enroll outpatient subjects of both genders aged 18-45 years with verified diagnoses of somatoform, stress-related and other neurotic disorders (F43, F45, F48) and signs of clinically relevant anxiety according to The Hospital Anxiety and Depression scale (HADS). After signing information sheet (informed consent form) to participate in the clinical study the subject will be interviewed (complaints, medical history, concomitant therapy) and physical examination will be performed; the subject will fill HADS scale. Degree of anxiety at screening should be ≥ 11 according to HADS. Where the subject meets inclusion criteria and has no exclusion criteria he/she will be enrolled into the study. The investigator will determine degree of anxiety using HAM-A scale; the subject will fill EQ-5D-3L questionnaire. At Visit 1 (Day 1) the subject will be randomized into one of the follow treatment groups:

- Group 1: Tenoten[®] at 2 tablets twice daily (4 tablets/day);
- Group 2: Placebo at 2 tablets twice daily (4 tablets/day);
- Group 3: Tenoten® at 2 tablets 4 daily (8 tablets/day).
- Group 4: Placebo at 2 tablets 4 daily (8 tablets/day).

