- 8. Personality and behavioural disorders at mature age (F60-69).
- 9. Mental deficiency (F70-79).
- 10. Inflammatory and traumatic injuries of brain with persistent neurological deficit.
- 11. Prior diagnosis of heart failure defined by the New York Heart Association classification (1964) as III or IV FC.
- 12. Malignant neoplasm/suspected malignant neoplasm
- 13. Patients allergic to/intolerant of any constituent of the medications used in the treatment.
- 14. Malabsorption syndrome, including congenital or acquired lactase deficiency (or any other disaccharidase deficiency) and galactosemia.
- 15. Any conditions which, according to the investigator, may interfere with the subject's participation in the study.
- 16. Scheduled hospiralizations, surgeries during the study.
- 17. Patients who, from the investigator's point of view, will not comply with the observation requirements of the study or adhere to study drug dosing regimens.
- 18. Use of any medicine listed in the section "Prohibited concomitant treatment" within 30 days preceding the inclusion in this study.
- 19. Drug addiction, alcohol usage in the amount exceeding 2 units of alcohol per day³.
- 20. Pregnancy, breast-feeding.

² Acceptable contraception includes intrauterine device; barrier method (condom, contraceptive cap, cervical cap or spermicide), previous surgical sterilization or vasectomy (for male subjects or partners). Throughout the study systemic hormonal contraceptives including oral contraceptives will not be allowed.

³1 unit of alcohol is equivalent to 0.33 L of lager/150 mL of unfortified wine, or 40 mL of a spirit

- 21. Participation in other clinical trials in the previous 3 months.
- 22. Patients who are related to any of the on-site research personnel directly involved in the conduct of the trial or are an immediate relative of the study investigator. 'Immediate relative' means husband, wife, parent, son, daughter, brother, or sister (regardless of whether they are natural or adopted).
- 23. Patients who work for OOO "NPF "Materia Medica Holding" (i.e. the company's employees, temporary contract workers, appointed officials responsible for carrying out the research or immediate relatives of the aforementioned).

Criteria for Withdrawal or Termination

- 1. Participant's failure or decline to comply with the protocol requirements.
- 2. Necessity for prescribing medications not permitted during the study.

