- 3. An adverse event requiring discontinuation of the study product;
- 4. Pregnancy.
- 5. Patient's decision to withdraw early for lack of efficacy or other reasons.
- 6. Eligibility error.
- 7. Cases not stipulated in the protocol where the investigator decides that further participation may harm the patient.

Number of subjects

It is planned to include 390 subjects, which is expected to yield at least 310 patients completing all protocol procedures.

Interim analysis

An interim statistical analysis is not scheduled within the study.

Treatment

Group 1

Name of the medicinal product: Tenoten

Active ingredient: Affinity purified antibodies to brain-specific S-100 protein - 0.003 g*

* applied onto lactose as a water-alcohol mixture containing no more than 10^{-15} ng/g active form of the API.

Excipients: Lactose monohydrate (lactose) - 0.267g (Eur. Ph.⁴, USP⁵ NF, BP⁶)

Microcrystalline cellulose - 0.03 g (Eur. Ph., USP NF, BP)

Magnesium stearate - 0.003 g (Eur. Ph., USP NF, BP)

⁴ Eur. Ph. European Pharmacopoeia (current edition)

⁵ USP – current US Pharmacopeia

⁶ EP – current European Pharmacopoeia

Method of administration: Tablet for oral use. Dose per administration: 2 tablets. 2 tablets twice daily (4 tablets/day). The tablets should be held in the mouth until dissolution, without meal.

Dosage form: Tablets.

Description: White to off-white, round, flat, scored on one side and beveled tablets.

Storage conditions: Store in a place protected from light at a temperature below 25 C. Keep out of the reach of children.

Group 2

Name of the medicinal product: Placebo

Active ingredient: NA

Excipients: Lactose monohydrate (lactose) - 0.267 g (Eur. Ph⁴., USP⁵ NF, BP⁶)

Microcrystalline cellulose - 0.03 g (Eur. Ph., USP NF, BP)

Magnesium stearate - 0.003 g (Eur. Ph., USP NF, BP)

Method of administration: Tablet for oral use. Dose per administration: 2 tablets. 2 tablets twice daily (4 tablets/day). The tablets should be held in the mouth until dissolution, without meal.

Dosage form: Tablets.

Description: White to off-white, round, flat, scored on one side and beveled tablets.

Storage conditions: Store in a place protected from light at a temperature below 25 C. Keep out of the reach of children.

Group 3

Active ingredient: Affinity purified antibodies to brain-specific S-100 protein - 0.003 g* * *applied onto lactose as a water-alcohol mixture containing no more than* 10^{-15} ng/g active form of the API.

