Procedure/visit	Visit 1 (Day 1)	Visit 2 (Week 4±3 days)	Visit 3 (Week 8±3 days)	Visit 4 (Week 12±3 days)
Informed consent	+			
Collection of complaints	+	+	+	+
Medical history	+			
Physical examination	+	+	+	+
HADS scale filling	+			
HAM-A scale filling	+	+	+	+
EQ-5D-3L questionnaire filling	+			+
Pregnancy test	+			
Concomitant therapy	+	+	+	+
Inclusion/exclusion criteria	+			
Randomization and prescription of study therapy	+			
Study drug supply	+	+	+	
Study drug accountability, compliance assessment		+	+	+
CGI scale filling				+
Evaluation of treatment safety		+	+	+

Schedule of study procedures

Statistical Analyses

Samples

Total set includes all the subjects who have signed ICF. This sample will consider all adverse events throughout the study, including those occurred prior to the study therapy.

The sample including all subjects who received at least one dose of the study product to be used for *analysis of the study treatment safety and tolerability* (*Safety population*), as all adverse events identified after the study product administration will be recorded.

Full Analysis Set This sample will consist of all enrolled subjects, except for those who met at least one of the following criteria:

- 1) failure to meet inclusion/non-inclusion criteria;
- 2) subject failing to take any dose of the study drug;
- 3) absence of any data on the subject after the study drug administration.

This was the best set for the Intention-to-treat method, so it will be used in the *Intention-to-treat efficacy analysis of the test therapy*.

Per Protocol set. This sample includes all subjects who completed the therapy as per the study protocol, without any missing visits or major protocol deviations. This set will be used in the *Per*

Protocol efficacy analysis of the test therapy.

Mean value of the total set for the relevant day will be used to fill lacking/missing data.

Data treatment and all statistical calculations under the protocol will be made using SAS-9.4 statistical software.¹⁰

Evaluation of sample size

The sample size was assessed in accordance with the following rules and assumptions:

- 1. Statistical assumptions
 - 1.1 the power of statistical tests 'P = (1β) ' is 80% (the probability of correct rejection of the null hypothesis is 0.8)
 - 1.2 the probability of type 1 error 'a' is less that 5% (the probability of false acceptance of the alternative hypothesis is less than 0.05);

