where μ_{T1} – mean reduction (initial – final score) of HAM-A total score in Tenoten group with dosing scheme 2 tablets 2 times a day, μ_{T2} – mean reduction (initial – final score) of HAM-A total score in Tenoten group with dosing scheme 4 tablets 2 times a day, δ – equivalence margin accepted as 0.15*M where M – mean total population score at baseline;

- 1.9 calculation of sample size for statistical criteria will be made using the group of formulas:
 - 1.9.1. calculation of sample size to evaluate superiority of the study product over placebo:

$$n_1=n_2=\frac{2(z_{\alpha/2}+z_\beta)^2\sigma^2}{\epsilon^2}$$

where $\mathbf{n_1}$, $\mathbf{n_2}$ is sample size for the study product group; ε – expected difference in mean reduction of the total score between Placebo and Tenoten groups; $\boldsymbol{\sigma}$ – standard deviation of mean reduction of the total score (calculated as standard deviation of difference between two uncorrelated random variables); $z_{\alpha/2}$ – tabular value of two-sided z-test for α value; z_{β} – tabular value of one-sided ztest for β value;

1.9.2. calculation of sample size for equivalence evaluation:

$$n_1 = n_2 = \frac{2(z_{\alpha} + z_{\beta/2})^2 \sigma^2}{(\delta - |\epsilon|)^2},$$

where $\mathbf{n_1}$, $\mathbf{n_2}$ is sample size for the study product group; ε – expected difference in mean reduction of the total score between Tenoten with dosing scheme 2 tablets 2 times a day and Tenoten with dosing scheme 4 tablets 2 times a day; $\boldsymbol{\sigma}$ – standard deviation of mean reduction of the total score (calculated as standard deviation of the difference between two uncorrelated random variables); z_{α} – tabular value of z-test for α value; z_{β} – tabular value of z-test for β value, δ – equivalence margin accepted as 0.15*M where M – mean total population score at baseline;

1.10 sample size will be determined using the formula:

N_{PP}=max{ n_i, all pairs of interest (i)},

where N_{PP} – Per Protocol sample size; n_i – result of calculation in cl. 1.6, i.e. the result for each of the three study hypotheses;

1.11 final sample size will be determined using the formula:

$$N_T = N_{PP} / (1 - C_w),$$

where N_T – final sample size; N_{PP} – result of calculation in cl. 1.7, i.e. the scheduled number of the subjects completing the study per protocol; C_w – withdrawal coefficient.

2. Assumptions on expected clinical study effects:

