Mean HAM-A total score at 12 weeks of therapy in Tenoten groups with both dosing schemes is expected to reduced by at least 10 units, in Placebo - by no more than 6 units (difference – at least 4 points). Population variance for total score change was $\sigma^2=44$ (based on preliminary analysis).

HAM-A mean score changes after 12 weeks in Tenoten groups for both dosing schemes are expected to differ by less than **3** points. Population variance was accepted as 6^2 =44 (based on preliminary analysis).

According to the statistical criteria and the assumptions above, for evaluation of differences in various dosing schemes, group size will be **103** subjects for Tenoten group (each dosing scheme) and **52** subjects for Placebo group (each dosing scheme). To evaluate superiority of the study product over placebo at different dosing schemes the group size will be 58 subjects for Tenoten group (each dosing scheme) and 26 subjects for Placebo group (each dosing scheme). The final sample size will be **103** subjects for Tenoten groups (each dosing scheme) and **52** subjects for Placebo group (each dosing scheme).

Given potential withdrawal of at least 20% subjects during the study for various reasons, at least **390** subjects will be required to sign informed consent.

Statistical criteria

All statistical calculations will be made using two groups of statistical criteria:

- parametric to evaluate continuous and interval random values;
- nonparametric to obtain:
 - evaluations of equality/inequality of proportions of the subjects upon their comparison for various visits,

- analysis of frequencies of the features compared, and
- evaluation of continuous and interval random values in case of non-compliance with normal random distribution.

Parametric criteria

Prior to analysis using parametric statistics, data samples under comparison will be tested for normality (the Kolmogorov-Smirnov test). Data normalizing transformations (e.g. Box-Cox, Yeo-Johnson etc.) would be applied if necessary.

The following parameters and approaches are to be used:

- 1. To evaluate the differences in continuous variables obtained in one group at two different visits Student's test for matched samples.
- 2. To evaluate time changes in parameters compared analysis of variance (ANOVA) or modified repeated measures covariance (ANCOVA).

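### Filling missing HAM-A scores in the Full Analysis Set with one mean pooled over all arms raises the false-equivalence rate to roughly 1.5 to 5 times nominal and shrinks the drug effect

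*Combined protocol and SAP*

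**What the plan says.** Under Statistical Analyses, Samples, the missing-data rule is one sentence: "Mean value of the total set for the relevant day will be used to fill lacking/missing data". The same section defines the set it refers to: "Total set includes all the subjects who have signed ICF". The mean is therefore taken over all arms.

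The FAS is used for the intention-to-treat efficacy analysis. It drops only subjects who fail eligibility, take no dose, or have no data after dosing. Anyone who withdraws later stays in and has to be filled. The Per Protocol (PP) set contains subjects who completed therapy "without any missing visits or major protocol deviations", so nothing is filled there.

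Equivalence of the two doses is hypothesis 1.8.3, one of three that share alpha (0.05/3 each, item 1.7). The margin is described as "equivalence margin accepted as 0.15*M where M" is the mean baseline score; no number is given for M. The withdrawal criteria include "Patient's decision to withdraw early for lack of efficacy or other reasons" and "Necessity for prescribing medications not permitted during the study". The sample-size section expects substantial loss: "Given potential withdrawal of at least 20% subjects during the study for various reasons". Secondary endpoint 4 is "Proportion of subjects with lack of anxiety (<14 points according to HAM-A scale".

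**The concern.** A value pooled over arms pulls every arm towards the common mean. For a superiority test that costs effect size. For an equivalence test it works in favour of the claim: the estimated dose difference shrinks and the margin does not. The reported standard error (SE) describes the shrunken estimator correctly, so nothing in the output would reveal the problem.

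There are two further effects. If missingness differs between arms, the fill can create a difference that does not exist. And a subject who leaves for lack of efficacy, or because a prohibited drug is needed, is given the average Week 12 score and may be counted as a success on the <14 endpoint.

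At stake are the error rate of a formal, alpha-sharing hypothesis and the accuracy of the intention-to-treat estimate of the drug effect.

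**Working it through.** **Inputs from the plan.** Variance of HAM-A change 44; mean reductions 10, 10 and 6; allocation 2:2:1:1 with placebo pooled; alpha 0.05/3 = 1.67%, one-sided for equivalence; baseline and final scores treated as uncorrelated (item 1.9), so each contributes variance 22.

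**Assumptions.** Margin 3, because 0.15·M has no number. FAS missingness of 5–20%, equal across arms and random: the plan's 20% links 390 consented subjects to 310 completers and is not a FAS figure. FAS of 129/129/130, from 103/0.8 and 104/0.8.

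**Reproducing the plan's sizes.**
- Equivalence: 2 × (1.960 + 1.282)² × 44 / 3² ≈ 102.8, so 103, as stated. A value of 3 for the margin less the expected difference therefore fits the plan, and 3 = 0.15 × 20 implies M = 20 if the expected difference is zero. This uses one-sided 0.025; the plan's own 0.05/3 in formula 1.9.2 gives 2 × (2.128 + 1.282)² × 44 / 9 ≈ 113.7, so 114.
- Superiority: 2 × (2.394 + 0.842)² × 44 / 4² ≈ 57.6, so 58, as stated.
- Dropout: 310 / 0.8 = 387.5, consistent with 390.

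**False equivalence, analytic.** With share w filled, a true difference of 3 is estimated as 3(1 − w). A filled subject's change is own baseline minus a constant, with variance 22, so

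SE = √{2 × [44(1 − w) + 22w] / 129}.

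Equivalence needs an estimate below 3 − 2.14 × SE, where 2.14 is the one-sided t quantile at 0.05/3. The probability is Φ{[3 − 2.14·SE − 3(1 − w)] / SE}.

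| w | Mean estimate | SE | Cut-off | False equivalence | Simulated |
|---|---|---|---|---|---|
| 5% | 2.85 | 0.816 | 1.25 | 2.5% | 2.3–2.6% |
| 10% | 2.70 | 0.805 | 1.28 | 3.9% | 3.8–4.0% |
| 15% | 2.55 | 0.794 | 1.30 | 5.8% | 5.8–6.1% |
| 20% | 2.40 | 0.784 | 1.32 | 8.5% | 8.1–8.4% |

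The last column comes from 20,000 simulated trials per setting, with baseline–Week 12 correlation 0 and 0.5. Observed data without the fill gave 1.5–1.9%. As multiples of 1.67%, the simulated rates run from about 1.4–1.6 at 5% missing to about 5 at 20%.

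At 20% missing the simulated SE of the dose difference is 0.79 as reported and 0.78 in truth. On observed data it is √(2 × 44 / 103.2) = 0.92.

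**Sensitivity.** For M = 15 to 30 (margin 2.25 to 4.5), false equivalence is 2.3–3.2% at 5% missing, 3.3–5.5% at 10% and 5.8–16.0% at 20%. At one-sided 0.025, the level that gives 103, it is 3.9%, 6.0% and 11.4% at 5%, 10% and 20% missing (margin 3, 130 per arm).

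**Drug effect.** 4 × (1 − w) = 3.8, 3.6 and 3.2 at 5%, 10% and 20%. Coverage of the 95% confidence interval is 94%, 92% and 83%. Superiority type I error stays at 1.6–1.7%, and power at 20% missing is 95.1% against 97.1% on observed data.

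**Unequal missingness.**
- With 15% missing on drug and 30% on placebo, the fill corresponds to a reduction of (0.85 × 20 + 0.70 × 6) / 2.40 = 8.83. The effect is then (8.5 + 0.15 × 8.83) − (4.2 + 0.30 × 8.83) = 2.98, with coverage 75%.
- For two equal doses with 10% and 30% missing (and, say, 20% on placebo), the spurious difference is 0.20 × (10 − 8.67) = 0.27; simulation gave about 0.26.

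**The <14 endpoint.** The average improvement credited is (2×10 + 2×10 + 6 + 6) / 6 = 8.67. With M = 20 the filled score is 20 − 8.67 = 11.3, so every filled subject counts as free of anxiety. That holds for M below 14 + 8.67 = 22.67. Above it, every filled subject counts as a failure.

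**The case against.** The strongest reply is that a PP efficacy analysis, untouched by the fill, is already planned, and that items 1.10–1.11 size the trial on PP completers. If equivalence had to hold in both sets, false equivalence would stay near nominal even with the fill left in: 1.5–1.9% at 5–20% missing, taking PP as the observed cases. This stands as far as it goes. But sizing on completers does not say which set decides, no such joint rule is written, and the FAS estimates would still be biased.

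Other points stand as limits:
- The margin is assumed, and 20% missing within the FAS may be too high. With 103 per arm the 20% figure was 7.1% in one simulation and about 8.0% in another.
- At the plan's own alpha, coverage of 98.3% intervals is about 97.6%, 96.9% and 91.5% at 5%, 10% and 20% missing, a smaller shortfall than the 95% intervals suggest.
- The spurious difference of 0.26 points is minor, about 9% of the assumed margin.
- The <14 result reverses for M above about 22.7, and the plan does not say outright that the fill applies to binary endpoints.
- All simulated figures use random missingness, so the harm from outcome-related withdrawal is described but not measured.

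**Conclusion.** The concern holds. This is a stated rule that gives a wrong answer when followed, and it needs correcting before the analysis. In the FAS it raises false equivalence from 1.67% to about 2.3–2.6% at 5% missing and 8.1–8.4% at 20%. It also shrinks the drug effect by exactly the missing share when missingness is equal across arms. The size depends on the assumed margin of 3, equal random missingness and the FAS deciding equivalence. The direction of the equivalence error is the same at every margin from 2.25 to 4.5. The superiority tests keep their type I error; what suffers there is the estimate and its confidence interval.

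**What to change.** - Delete the mean-fill sentence.
- State which set decides equivalence; it should have to hold in both the FAS and the PP set.
- Analyse HAM-A in the FAS without any fill. One suitable choice is a likelihood-based repeated-measures mixed model on all observed Week 4, 8 and 12 scores, adjusted for baseline HAM-A. Amend item 4 of Parametric criteria, which reserves mixed models for non-normal data.
- Do not use the pooled mean to classify withdrawn subjects on the ≥50% and <14 endpoints; counting them as non-responders is one option.
- Add a sensitivity analysis that shifts imputed values against each claim: against superiority, and away from equivalence. The mixed model alone does not deal with withdrawal that depends on unobserved outcomes.

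The cost is analysis wording only; PROC MIXED is already listed and no extra subjects or visits are needed. FAS intervals become wider: the dose-difference SE is about 0.92 instead of 0.79 at 20% missing, before any gain from the Week 4 and 8 data.

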Excipients: Lactose monohydrate (lactose) - 0.267g (Eur. Ph.⁷, USP⁸ NF, BP⁹)

Microcrystalline cellulose - 0.03 g (Eur. Ph., USP NF, BP)

Magnesium stearate - 0.003 g (Eur. Ph., USP NF, BP)

Method of administration: Tablet for oral use. Dose per administration: 2 tablets. 2 tablets 4 times daily (8 tablets/days). The tablets should be held in the mouth until dissolution, without meal.

Dosage form: Tablets.

Description: White to off-white, round, flat, scored on one side and beveled tablets.

⁷ Eur. Ph. European Pharmacopoeia (current edition)

⁸ USP – current US Pharmacopeia

⁹ EP – current European Pharmacopoeia

Protocol No. MMH-TN-001 19-Apr-2016 Storage conditions: Store in a place protected from light at a temperature below 25 C. Keep out of the reach of children.

Group 4

Name of the medicinal product: Placebo

Active ingredient: NA

Excipients: Lactose monohydrate (lactose) - 0.267 g (Eur. Ph⁴., USP⁵ NF, BP⁶)

Microcrystalline cellulose - 0.03 g (Eur. Ph., USP NF, BP)

Magnesium stearate - 0.003 g (Eur. Ph., USP NF, BP)

Method of administration: Tablet for oral use. Dose per administration: 2 tablets. 2 tablets 4 times daily (8 tablets/days). The tablets should be held in the mouth until dissolution, without meal.

Dosage form: Tablets.

Description: White to off-white, round, flat, scored on one side and beveled tablets.

Storage conditions: Store in a place protected from light at a temperature below 25 C. Keep out of the reach of children.

Treatment duration

Tenoten/Placebo treatment duration is 12 weeks.

Observation period

In total the patients will be monitored for 12 weeks.

Symptomatic (Standard) treatment

Subjects are allowed to receive medications used to treat coexisting diseases other than those representing exclusion criteria, except drugs listed in section "Forbidden concomitant therapy".

Prohibited concomitant therapy

Within 4 weeks prior to enrollment and during the study (beginning from signing informed consent form and initiation of screening) subjects are not allowed to receive any medications that may affect mental and emotional status (parenthesized is the ATC group):

- 1. Psycholeptics (ATC group N05), including antipsychotics, anxiolytics (tranquilizers), hypnotics and sedatives.
- 2. Psychoanaleptics (ATC group N06) including antidepressants, psychostimulants, nootropic drugs and their combinations.
- 3. Antiepileptic drugs (ATC group N03A).
- 4. Anticholinergic drugs (ATC group N04A).

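### The sample-size text applies 390 to subjects signing consent, although the arithmetic behind it (310/0.8) allows only for withdrawal and fits the number included or randomised

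*Combined protocol and SAP*

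**What the plan says.** The protocol summary, under Number of subjects, states: "It is planned to include 390 subjects, which is expected to yield at least 310 patients completing all protocol procedures".

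The last paragraph of item 2 under Evaluation of sample size reads differently. It begins "Given potential withdrawal of at least 20% subjects during the study for various reasons" and concludes that at least 390 "subjects will be required to sign informed consent".

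The protocol treats these as two populations. Under Study design, consent comes first, followed by interview, examination and the HADS. Only then: "Where the subject meets inclusion criteria and has no exclusion criteria he/she will be enrolled into the study". Under Samples, "Total set includes all the subjects who have signed ICF", while the Full Analysis Set starts from enrolled subjects.

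Item 1.11 gives the inflation as N_T = N_PP/(1 − C_w). N_PP is "the scheduled number of the subjects completing the study per protocol" and C_w is a withdrawal coefficient. No term for screening failure appears. Item 1.1 sets the power: it "is 80% (the probability of correct rejection of the null hypothesis is 0.8").

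**The concern.** Consent and inclusion are separated by a real screen: HADS anxiety of at least 11, HADS depression below 11, a washout of prohibited medicines and 23 exclusion criteria. Some consented subjects will not be randomised. A number that allows only for later withdrawal is therefore too small as a consent target if the expected completers are to be reached.

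The comparison exposed to this is the equivalence of the two dosing schemes. It sets the sample size (103 per Tenoten arm against 58 for superiority) and has almost no reserve above 80% power.

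A second wording point bears on the same promise. Withdrawal of at least 20% makes 390 × 0.8 = 312 the largest possible number of completers, whereas the summary offers at least 310 as a minimum.

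**Working it through.** **Inputs from the documents.** 103 subjects per Tenoten arm and 52 per placebo arm; withdrawal 20%; variance 44; superiority difference 4; difference between schemes 3; power 80%; α = 0.05/3; superiority two-sided, equivalence one-sided.

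**Assumptions.**
- Screening-failure rates of 5%, 10% and 20%; none is given.
- An equivalence margin of 3. The plan defines the margin as 0.15 × M without a value for M, and gives 3 only as the bound on the expected difference. A margin of 3 corresponds to M = 3/0.15 = 20.
- No true difference between the two schemes.
- One-sided α of 0.025 for equivalence, because it reproduces 103; the documents do not state it.

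**1. Reproducing the plan's figures.**
- Completers: 2 × 103 + 2 × 52 = 310.
- Inflation: 310/(1 − 0.20) = 387.5, so 388, which the plan rounds to 390. Inflating arm by arm gives the same: 2 × 129 + 2 × 65 = 388.
- Equivalence, printed formula: 2(1.960 + 1.282)² × 44/3² = 102.7, so 103.
- Superiority: 2(2.394 + 0.842)² × 44/4² = 57.6, so 58 per arm at two-sided 0.05/3.

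**2. Completers if 390 is the number consenting.** With f screening failures, completers = (390 − f) × 0.8.

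| Failures f | Completers |
|---|---|
| 0 | 312.0 |
| 1 | 311.2 |
| 2 | 310.4 |
| 3 | 309.6 |

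The rounding from 388 to 390 absorbs two failures; the third takes the expected number below 310.

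**3. Power at assumed failure rates.** The number per Tenoten arm is n = completers × 103/310. Equivalence power is 2Φ(3/√(2 × 44/n) − 1.960) − 1. Superiority compares each Tenoten arm with pooled placebo (each about one third of completers) at two-sided 0.05/3.

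| Failure rate | Randomised | Completers | n per Tenoten arm | Equivalence power | Superiority power |
|---|---|---|---|---|---|
| 0% | 390 | 312 | 103.7 | 80.5% | 97.5% |
| 5% | 370.5 | 296 | 98.5 | 77.5% | 96.7% |
| 10% | 351 | 281 | 93.3 | 74.1% | 95.8% |
| 20% | 312 | 250 | 82.9 | 65.9% | 93.3% |

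Taking exactly one third of completers per Tenoten arm instead gives 80.7%, 77.7%, 74.3% and 66.2% for equivalence. Equivalence power first drops below 80% at the fourth failure (103/310 share) or the fifth (one-third share).

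**4. Superiority reserve.** Power reaches 80% at 58 per arm: 58 × 3 = 174 completers, 174/0.8 = 217.5 randomised, and 1 − 217.5/390 = 44% screening failure.

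**5. Consents needed for 388 randomised.** 388/(1 − s) gives 409, 432 and 485 at s = 5%, 10% and 20%.

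**6. The withdrawal wording.** With 390 randomised, 310 completers allow at most 80 withdrawals: 80/390 = 20.5%. A rate of 20% is thus close to the upper limit that the promise tolerates, not a lower limit.

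**The case against.** The strongest reply is that the two passages are compatible. The sample-size text sets a minimum number of consents, and if 390 are included then at least 390 have necessarily signed. On the summary's reading, 390 yields 312 completers and nothing is lost. This stands to the extent that the shortfall is conditional. A reader might infer that the passages set two different points at which recruitment stops, but neither states a stopping point. What remains is that a minimum of 390 consents is too low once more than two subjects fail screening, and it is the only consent figure given.

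A second reply is that the 20% may already cover screening losses. The section on prohibited concomitant therapy describes the period "during the study (beginning from signing informed consent form and initiation of screening"), and eligibility error is a listed reason for withdrawal. That reading is possible, but the sentence concerns prohibited medicines, and item 1.11 calls C_w only a withdrawal coefficient. If the 20% did run from consent, 390 would be a consent count and the summary's 390 included would be the wrong label. The passages would still need reconciling.

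A third reply is that withdrawal of at least 20% is loose phrasing, since the calculation plainly used exactly 20%. That is fair; it is a wording correction, and the arithmetic itself reproduces.

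**Conclusion.** The point holds as an inconsistency in which population 390 describes, with a conditional effect on size. The derivation supports 390 as the number included or randomised; the sample-size text gives it as the number consenting, without an allowance for screening failures. If it were used that way, failure rates of 5% to 20% would leave about 296 to 250 completers and equivalence power of about 77–78% down to 66%, against about 80.5% with none. These figures rest on the assumed failure rates, margin of 3, zero true difference and one-sided 0.025.

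Three stronger readings are not supported:
- **That any single screening failure breaks the plan.** Rounding absorbs two failures for the 310 completers and three or four for 80% equivalence power.
- **That the trial as a whole loses its 80% power.** Only equivalence does. Both superiority comparisons stay above 90% at these failure rates.
- **That the lower power at α = 0.05/3 comes from screening loss.** At that level equivalence power is about 74% with no failures at all, because the printed equivalence formula then gives 2(2.128 + 1.282)² × 44/3² = 113.7, so 114 per arm instead of 103. That is a separate problem. Screening loss of 5% adds only about 4 percentage points to it.

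**What to change.** In the last paragraph of item 2 under Evaluation of sample size, state that 390 is the number randomised, in agreement with Number of subjects, and that consents are counted separately. In the same sentence, change withdrawal from at least 20% to up to 20%, so that it agrees with at least 310 completers. A consent target, if one is wanted, should carry its assumed screening-failure rate.

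If 390 consents is really intended, correct Number of subjects instead, and restate the expected completers and equivalence power for a stated screening-failure rate.

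The cost is a sentence of text. In practice it means somewhat more screening if sites had planned on 390 consents (about 19 more at 5% failure and 42 more at 10%, from 409 − 390 and 432 − 390). Under the alternative, the cost is a slightly lower stated power.
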